8.6 SAFETY PARAMETERS

Adverse Events

Number and percent of eyes will be summarized for each reported ocular AE at the operative visit and each postoperative visit. Serious ocular AEs and the non-ocular serious AEs will be summarized in the same manner. Additionally, for each of the device related AE reported during the study, the number and percent of study eyes reported with the event will be presented. For each reported AE, a two-sided 95% confidence interval will be provided for the percent of eyes reported with the AE during the study (i.e. at \leq 6 months.)

Each ISO defined cumulative and persistent adverse events at Postop Month 6 will be summarized per ISO 11979-7:2014 (E) using count and percent of subjects reported with such event. The maximum number of cases allowed before the ISO-defined SPE rate of each adverse event will be calculated. For each ISO adverse event, if the observed incidence for the LAL eye group is at most the maximum number of cases, it can be concluded that the LAL does not have a rate higher than the corresponding ISO-defined SPE rate.

The cumulative and persistent adverse events during the 6-month follow-up period will also be stratified by age (per quartiles) and study sites.

Change in BCDVA

Change in BCDVA from Postop Week 3 or from Preoperative will be presented at each visit as categorical outcomes of "Increase in 15 letters or more", "Increase in 10-14 letters", "Increase in 5-9 letters", "No change", "Decrease in 5-9 letters", "Decrease in 10-14 letters", and "Decrease in 15 letters or more". The 90% confidence interval (corresponding to the one-sided test recommended by the ISO 11979-7 for cumulative and persistent adverse events) for the percent of eyes with a BSCVA loss of \geq 10 letters will be calculated per binomial distribution. The mean change in logMAR BCDVA from Postop Week 3 or Preoperative with the 95% confidence interval for the mean will also be presented. Similarly, the mean change from the prior visit to the next visit will also be summarized in the same manner.

The listing of BCDVA and the possible reason for BCDVA loss of 10 letters or more will be provided for the eyes reported with a 10-letter or more loss in BCDVA during the study (i.e. from preoperative visit or previous visit).

Distance Corrected Contrast Sensitivity

For the contrast sensitivity (in log units) at each spatial frequency level under each of the four test conditions (photopic with and without glare and mesopic with and without glare) at Postop Week 3 and Postop Month 6 will be summarized by mean, standard deviation, median, minimum and maximum for the eyes participated in the contrast sensitivity substudy. The number and percent of eyes that cannot see any plate will be presented.

The mean of "within-eye" loss of contrast sensitivity from Postop Week 3 to Postop Month 6 will be provided with the 1-sided 95% confidence interval for each spatial frequency. The percentage of eyes showing > 0.3 log unit loss at two or more spatial frequencies will be calculated.

Increased Astigmatism

Number and percent of eyes with increased astigmatism from Postop Week 3 will be reported at each postoperative visit

Subjective Symptoms and Complaints

Number and percent of eyes will be summarized for each reported subjective symptom.

Other Ocular Examinations

Slit lamp and fundus exam findings and IOP including changes will be summarized descriptively. Number of subjects with fundus exam changes from the pre-op and Postop Week 3 evaluation will be summarized.

Endothelial Cell Density (ECD) and Morphology Data

Specular Microscopy data includes endothelial cell density, hexagonality and coefficient of variation. These endpoints will be summarized by mean, standard deviation, 95% CI of the mean, minimum and maximum. The change in ECD and percent change in ECD from preoperative will be summarized in the same manner. Additionally, ECD change and ECD percent change for each eye will be calculated between Preoperative and Postop Week 3 and between Postop Week 3 and Postop Month 6. These changes will be summarized by mean, standard deviation, 95% CI for mean, minimum, and maximum. Additionally, at Postop Week 3 and Postop Month 6, the number and percent of eyes with an ECD of < 1500 cells/mm² and number and percent of eyes with an ECD change from baseline \leq -25% (i.e. and an ECD loss of \geq 25%) along with the 95% confidence interval of the percentage derived per binomial distribution will be calculated for the LAL eyes and Control eyes separately.

The percent ECD loss (%ECL) at Postop Month 6 for each eye and the difference between %ECL (Δ %ECL) at Postop Month 6 for each subject are derived as follows:

%ECL = (ECD at Preop – ECD at Postop Month 6)
$$\div$$
 ECD at Preop × 100% Δ %ECL = %ECL of LAL eye - %ECL for Control eye

The descriptive statistics for continuous variables will be used to summarize Δ %ECL. A one-sided 95% upper confidence limit for mean Δ %ECL will be derived based on t-distribution. If the Nichamin III foldable lens inserter is used during the study, the analyses may be stratified by the subjects with versus without the use of Nichamin III foldable lens inserter.

It should be noted that, per the previous PMA clinical study, the standard deviation of $\Delta\%$ ECL is estimated as 4%. For a statistical hypotheses test of H0: Mean of $\Delta\%$ ECL $\geq 5\%$ versus Ha: Mean of $\Delta\%$ ECL < 5% (i.e. the mean of %ECL in the LAL eyes is at most 5% higher than that in the control eyes) with a one-sided significance level of 0.05, a sample size of 100 bilateral subjects at 6 months can provide the following statistical power at different true values of Mean of $\Delta\%$ ECL. The derived one-sided 95% upper confidence limit of mean $\Delta\%$ ECL described above can be used to compare against the 5% used in the statistical hypotheses described above.

True µ∆%ecl	Statistical Power
0.0%	>0.99
0.5%	>0.99
1.0%	>0.99
1.5%	>0.99
2.0%	>0.99

2.5%	>0.99
3.0%	>0.99
3.5%	0.98
4.0%	0.80

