These more variable results contrast with non-LASIK patients undergoing cataract surgery with traditional monofocal IOLs, where the percentage within \pm 0.5 D of the predicted refraction can reach 80% or more depending on surgeon techniques and the patient population. In the Phase III study conducted under IDE G100240 in patients with low preoperative keratometric cylinder, 84% of control eyes implanted with a monofocal IOL were within \pm 0.5 D of the predicted MRSE. While the LAL group performed even better, with 91% within \pm 0.5 D, the main clinical benefit of this improvement in MRSE was a reduction in the number of outliers with significantly higher residual refractive errors. Because the number of such outliers is potentially much higher in post-LASIK eyes undergoing cataract surgery, these patients would likely see a larger clinical benefit by reducing the range of residual MRSE errors due to the inherent difficulties in predicting IOL power in this group. In addition, by producing the desired change in spherocylindrical power of the implanted Light Adjustable Lens (LAL), unanticipated post-operative astigmatism can also be addressed, potentially reducing the need for secondary surgical procedures for the vast majority of post-LASIK patients with residual refractive error.

To evaluate this potential, we propose to compare 6 months postoperative refractive and visual acuity data for LAL eyes compared to a control group of fellow eyes implanted with a commercially available monofocal IOL. Based on the anticipated range of post-operative residual MRSE being within the LAL adjustment range, similar final outcomes are anticipated when compared with the LAL group studied under IDE G100240.

2.1 CLINICAL STUDIES PERFORMED WITH PRIOR VERSION OF THE LIGHT ADJUSTABLE LENS AND LIGHT DELIVERY DEVICE

Phase III Study Conducted Under IDE G100240

A 600 eye prospective, randomized, controlled, multi-center clinical trial of the LAL and LDD designed to evaluate safety and effectiveness over a 12-month period was conducted at 17 sites. In addition to the visual correction of aphakia, reduction in residual spherocylindrical refractive error and improvement in uncorrected visual acuity were evaluated following LAL implantation and subsequent refractive adjustment of the LAL by the LDD.

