Eyes with \geq 0.75 and \leq 2.5 diopters (D) of keratometric cylinder were randomly assigned to receive either the LAL or a commercially available, posterior chamber, non-accommodating, control monofocal IOL. Six hundred eyes were implanted with 403 eyes randomized to the LAL group and 197 eyes to the Control group.

⁸ Hamill E, Wang L, Chopra H, Hill W, Koch D. Intraocular lens power calculations in eyes with previous hyperopic laser in situ keratomileusis or photorefractive keratectomy. J Cataract Refract Surg 2017; 43:189-194.

⁹ https://www.reviewofophthalmology.com/article/post-refractive-cataract-choosing-lens-and-target

Co-primary effectiveness endpoints included percent reduction in manifest cylinder, percent mean absolute reduction in manifest refraction spherical equivalent (MRSE), and rotation of the LAL. All primary effectiveness endpoints compared pre-adjustment (LAL) or 17-21 days (Control) to 6 months postoperatively and the first two endpoints compared results between the LAL and Control groups. All three co-primary effectiveness endpoints were met with a p-value <0.0001. The difference in means for percent reduction in manifest cylinder was 54.7%, with a p-value <0.0001. The difference in means for percent reduction in absolute MRSE was 41.1% with a p-value <0.0001. Rotation of the LAL of ≤5 degrees was observed in 96.1% of LAL implanted eyes with both the upper and lower bound of the 95% confidence interval exceeding the requirement of 90%.

100% of eyes in both the LAL and Control groups had BSCVA of 20/40 or better, exceeding the historic grid rate of 92.5% (ISO 11979-7). The incidence of sight-threatening complications and adverse events for the LAL and Control groups were also below the threshold rates calculated from the 1-year historical grid for intraocular lenses (ISO 11979-7, Ophthalmic implants- Intraocular lenses- Part 7: Clinical investigations) except for the category of Secondary Surgical Interventions (SSI), which was significantly higher than the historical rate (p<.05).

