7.3.1 SURGICAL PROCEDURE

The LAL will be implanted using standard microsurgical techniques.

No additional refractive procedures such as limbal relaxing incisions or PRK are allowed on the primary eye (LAL) until after the Postop Month 6 visit.

The surgical procedure will be performed as follows:

- 1. Prepare and drape the eye for surgery in accordance with standard surgical procedures.
- 2. A temporal clear corneal incision will be made using the surgeon's standard instrumentation and techniques.
- 3. Use viscoelastic as agreed upon within the standard regimen to fill the anterior chamber through the incision opening.
- 4. Perform an anterior circular capsulorhexis using standard technique. The capsulorhexis should be well-centered with a 360° overlapping capsular edge to minimize IOL tilt and decentration and longitudinal IOL shift. The capsulorhexis and/or nuclear fragmentation can be performed with a femtosecond laser. Precision pulse capsulotomy (PPC) can also be used to perform the capsulorhexis.
- 5. The surgeon will extract the cataract by phacoemulsification.
- 6. In the event of an intraoperative complication prior to implantation of the LAL, including posterior capsule rupture, zonular rupture, radial capsulorhexis tear, vitreous loss, iris trauma, corneal complications or any intraoperative abnormality that may affect the postoperative pupillary dilation, or the centration or tilt of the intraocular lens, do not implant the LAL.

[figure not shown]
- 8. Verify proper orientation of the LAL
- 9. Aspirate any residual viscoelastic from the eye using a preferred technique.
- 10. The wound may close without suturing. If the unsutured wound is not watertight, close it with a either a suture using standard technique or an ocular sealant (ReSure Sealant).
- 11. After completion of the surgery, postoperative medications should be administered per the agreed upon investigative site standard regimen.

12. The subject will be provided with two pairs of RxSight approved UV protective spectacles (one clear and one tinted) to protect the implanted LAL from extraneous sources of UV light. It is important to direct the subject to follow all instructions that are provided with the UV protective spectacles.

If a patch was used at the conclusion of surgery, the subject will wait for the surgeon to remove the patch. Once removed, the subject will begin wear of the UV protective eyewear as instructed.

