7.5 EXAMINATION SCHEDULE

Subjects who agree to participate in the study will return for the listed follow-up examinations:

Primary Study Eye (LAL)

Evaluation	
Preoperative OU	Maximum of 60 days prior to Operative LAL Visit
Operative LAL	Day 0, day of LAL surgery
Postop Day 1 LAL	Days 1 to 2 post-Operative LAL Visit
Postop Week 1 LAL	Days 7 to 14 post-Operative LAL Visit
Postop Week 3 LAL (Adjustment #1)	Days 17 to 24 post-Operative LAL Visit
Adjustment #2, if needed	3 to 7 days post Adjustment #1
Adjustment #3, if needed	3 to 7 days post Adjustment #2
Lock-in #1	3 to 7 days post final adjustment
Lock-in #2, if needed	3 to 7 days post lock-in #1
Postop Months 1-2	7 to 14 days post final lock-In
Postop Month 3 LAL	Days 60 to 90 post-Operative LAL Visit
Postop Month 6 LAL	Days 120 to 180 post- Operative LAL Visit
Postop Month 12, if needed	Days 330 to 420 post- Operative LAL Visit

Unscheduled visits falling outside the designated ranges for scheduled visits will be considered "interim" visits for data recording purposes and a report form will be completed.

Fellow Study Eye (Control)

Evaluation	
Operative Control	Minimum of 7 days post- Operative LAL Visit
Postop Day 1 Control	Days 1 to 2 post-Operative Control Visit
Postop Week 1 Control	Days 7 to 14 post-Operative Control Visit
Postop Week 3 Control	Days 17 to 24 post-Operative Control Visit
Postop Month 3 Control	Days 60 to 90 post-Operative Control Visit
Postop Month 6 Control	Days 120 to 180 post- Operative Control Visit

Unscheduled visits falling outside the designated ranges for scheduled visits will be considered "interim" visits for data recording purposes and a report form will be completed.

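### Section 8.6 concludes on the LAL's cumulative adverse event rates from counts to Month 6, against ISO rates whose only stated time base is one year

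*Combined protocol and SAP*

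**What the plan says.** Section 8.6 (Safety Parameters, Adverse Events) says: "Each ISO defined cumulative and persistent adverse events at Postop Month 6 will be summarized per ISO 11979-7:2014 (E". For each ISO event a maximum number of cases is to be calculated from the ISO safety and performance endpoint (SPE) rate. If the LAL group has no more cases than that, the plan concludes that the LAL rate does not exceed the SPE rate. The section gives no time base for the SPE rates and no adjustment for length of follow-up.

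Section 7.5 sets the Month 6 visit for the LAL eye at "Days 120 to 180 post- Operative LAL Visit". The Month 12 visit takes place only if needed, is scheduled for LAL eyes only, and is not part of the ISO summary.

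Section 2.1 describes the earlier Phase III study as "designed to evaluate safety and effectiveness over a 12-month period was conducted at 17 sites". It reports that study's adverse events as "below the threshold rates calculated from the 1-year historical grid for intraocular lenses", "except for the category of Secondary Surgical Interventions (SSI), which was significantly higher than the historical rate".

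On secondary surgical interventions (SSIs), Section 7.3.1 says that no additional refractive procedures, with limbal relaxing incisions and PRK as examples, "are allowed on the primary eye (LAL) until after the Postop Month 6 visit". Sections 4 and 7.4 permit an SSI on the Control eye for complaints of anisometropia above 1.5 D after a refractive surprise. The table in Section 9.1 defines secondary IOL intervention as exchange, removal or reposition.

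**The concern.** The earlier study set 12 months of follow-up against what the protocol calls a one-year grid, so numerator and benchmark had the same horizon. This study sets 4 to 6 months of follow-up against rates from the same standard. A cumulative count can only stay level or rise with time. If the benchmark allows for a full year of events, the rule gives the LAL a year's allowance for part of a year's exposure.

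This matters because Section 8.6 states a conclusion, not only a display, and safety is part of the primary objective in Section 3. A lens with a one-year cumulative rate above the ISO rate could be declared no worse because some of its events had not yet occurred. More eyes would not cure this, because the fault is in the time base and not in precision.

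**Working it through.** **The plan's own figures.** The documents give no ISO rate, maximum case number or power for this comparison. The one figure that enters it is the number of eyes at Month 6. Section 8.1 needs 60 low-cylinder subjects for uncorrected acuity (SD 0.32, difference 0.15, one-sided 0.0125, 90% power). An exact paired t calculation also gives 60. With 60% of subjects in that group, 60 / 0.60 = 100, so the 100 reproduces.

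**Share of a year covered.** 120/365 = 0.33 and 180/365 = 0.49.

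**Direction.** For the same eyes, the number with a cumulative event by Month 6 cannot exceed the number by Month 12. Against a fixed one-year maximum, the shorter count is therefore equally or more likely to pass. Persistent events have no such ordering: one present at Month 6 may have resolved by Month 12.

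**Illustration of size.** The inputs below that the documents do not give are assumptions.

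- n = 100 LAL eyes (Section 8.1).
- One-sided level 0.05, inferred from Section 8.6, which links a 90% interval to the ISO one-sided test.
- p0 = one-year SPE rate, assumed to be 0.5%, 1% or 3%.
- Maximum c = smallest c with P(X ≥ c + 1 | n, p0) ≤ 0.05, binomial.
- True one-year rate = 3 × p0.
- f = share of the year's events that fall by the Month 6 visit: 1 (all), 0.8 (most events early), 0.49 and 0.33 (even timing, seen on day 180 or day 120).
- Chance of flagging = P(X ≥ c + 1 | n, 3 × p0 × f).

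For p0 = 1%, P(X ≥ 3) = 0.079 and P(X ≥ 4) = 0.018, so c = 3. The event probabilities by Month 6 are 0.03 × 1 = 0.03, 0.03 × 0.8 = 0.024, 0.03 × 0.49 = 0.0147 and 0.03 × 0.33 = 0.0099. The other rates follow in the same way:

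| Assumed p0 | Maximum cases | f = 1 | f = 0.8 | f = 0.49 | f = 0.33 |
|---|---|---|---|---|---|
| 0.5% | 2 | 0.19 | 0.12 | 0.04 | 0.01 |
| 1% | 3 | 0.35 | 0.22 | 0.06 | 0.02 |
| 3% | 6 | 0.81 | 0.59 | 0.15 | 0.03 |

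The f = 1 column serves both for counting over a full year and for the case in which every event occurs before Month 6. In that case the short window loses nothing.

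**The case against.** **The time base is inferred.** Section 8.6 gives no horizon for the SPE rates. The one-year label is in background text on the earlier study, which cites ISO 11979-7 without an edition there, whereas Section 8.6 cites the 2014 edition. This stands, and the point has to be conditional. But the label is the only time base the documents offer, and leaving the horizon unstated is itself a gap in a rule that draws a conclusion.

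**Events after surgery come early.** Section 9.1 defines toxic anterior segment syndrome as arising within 24 to 48 hours, so even timing is unfavourable as a general assumption. The 0.33 share also needs every eye to be seen on the first day of the window. This stands: the true loss may be small, and it is nil for events that all fall before Month 6.

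**The rule is weak anyway.** With one-year counting, the chance of flagging a threefold excess at an assumed 1% rate is only 0.35. This is true, but it is a separate limitation and does not justify a mismatched horizon.

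**Safety was settled earlier.** Section 8.1 refers safety to the approved premarket application, Section 8.6 labels its counts as Month 6, and Section 8.2 summarizes the two groups separately. These features help a careful reader, but Section 8.6 still draws a fresh conclusion against the ISO rate.

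**A stronger reading on SSIs.** A reader might infer that the bar on refractive procedures in LAL eyes until after Month 6, with SSIs permitted in Control eyes, biases the ISO SSI count towards the LAL. A reader might add that the LAL exceeded this category before. The documents do not support either step. No section says that limbal relaxing incisions or PRK count as an ISO SSI event. The Section 9.1 definition does not list them, and the bar does not name exchange, removal or reposition. The Phase III sentence covers the LAL and Control groups together and does not attribute the SSI excess to the LAL. What remains is an unclear definition.

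**Conclusion.** The point holds for cumulative events, on the condition that the SPE rates are one-year rates. As written, the rule can then only be neutral or lenient to the LAL. The documents do not fix the size: they give neither the SPE rates nor the timing of events. In the illustration the loss ranges from none to most of an already modest chance of detecting a threefold excess.

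A reader might extend this to all ISO adverse events, since the plan treats cumulative and persistent events in one sentence. That goes too far, because a persistent event read at Month 6 might later resolve and the comparison could run against the LAL.

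The weakness is in the wording of a safety conclusion. It does not affect the effectiveness analyses or the sample size.

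**What to change.** In Section 8.6 and the SAP:

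1. State the time base of each SPE rate used.
2. Report cumulative and persistent events separately.
3. Where the SPE rate is a one-year rate, treat the Month 6 comparison of cumulative events as descriptive. Replace the conclusion about the LAL rate with a statement limited to events observed through Month 6.
4. Beside it, present the within-subject LAL versus Control comparison over the same period. Both eyes have a day 120 to 180 window counted from their own surgery, so the data are already collected.

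Separately, reconcile Sections 4, 7.3.1, 7.4, 8.6 and 9.1 on which procedures count as an SSI, and state the definition in the SSI table. The rules on refractive procedures differ between the two eyes, so that row needs the definition to be readable.

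The cost is wording in the protocol and SAP, with no added visit, procedure or data item. The downside is a narrower safety statement against the ISO grid.

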Per the previous PMA clinical study, the standard deviation of logMAR UCDVA at Postop Month 6 is 0.11 D for the LAL group and 0.17 for the control group. Assuming the UCDVA at Postop Month 6 of the two eyes of the same subject are independent, the estimated standard deviation of Δ UCDVA is 0.21 (= square-root of the sum of 0.11² and 0.17²). Again, a larger standard deviation, 0.32 (\sim 1.5 × 0.21) is used for the sample size calculation. Based on the one-sided one-sample t-test (i.e. paired t-test) with a significance level of 0.0125, a sample size of 60 subjects can provide a statistical power of 90% if the true μ_{Δ UCDVA is -0.15 (i.e. 1.5 lines).

2. UCDVA at Postop Month 6 for subjects with keratometric cylinder (Kcyl) < 0.75 D at the preoperative examination in both eyes

H0: $\mu_{\Delta UCDVA_L} = 0$ versus Ha: $\mu_{\Delta UCDVA_L} < 0$ with a one-side significance level of 0.0125, where $\mu_{\Delta UCDVA_L}$ is the mean $\Delta UCDVA$ at Postop Month 6 for subjects with Kcyl < 0.75 D (low cylinder) at the preoperative examination in both eyes.

Based on the same assumptions discussed in the Section above, the required sample size for the analysis is 60 subjects. It is estimated that about 60% of the subjects at Postop

Month 6 will have a preoperative KCyl of < 0.75 D. Therefore, $100 (= 60 \div 60\%)$ bilateral subjects at Postop Month 6 are needed for this endpoint

Study Sample Size

Based on the sample size calculation for the primary and secondary primary effectiveness endpoints above, a sample size of 100 bilateral subjects at Postop Month 6 will be sufficient for the study. With a drop-out rate of at most 10% within the 6-month follow-up period and possible postponed LDD treatment after postoperative 6 months, up to 110 bilateral subjects should be implanted with LAL in one eye and Control lens in the other eye. Considering possible intraoperative complications that prevent the LAL implantation, it is determined that the study should attempt implantation in up to 120 eligible bilateral subjects in order to have at least 100 bilateral subjects at Postop Month 6.

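### Section 8.6 reads a count at or below a maximum as proof that the LAL adverse-event rate is not above the ISO SPE rate; such a count shows only that no excess was detected

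*Combined protocol and SAP*

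**What the plan says.** Section 8.6 (Safety Parameters, Adverse Events) summarises each ISO cumulative and persistent adverse event at Postop Month 6. It then sets a rule: "The maximum number of cases allowed before the ISO-defined SPE rate of each adverse event will be calculated". If the LAL count is no more than that maximum, "it can be concluded that the LAL does not have a rate higher than the corresponding ISO-defined SPE rate".

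No SPE rate, formula or significance level is given for the maximum. The nearest indication is in the next part of 8.6, on change in BCDVA, where a 90% confidence interval is described as "corresponding to the one-sided test recommended by the ISO 11979-7 for cumulative and persistent adverse events".

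The same adverse-event text also plans a two-sided 95% confidence interval for each reported adverse event. That interval plays no part in the rule.

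On numbers, section 8.1 says that "up to 110 bilateral subjects should be implanted with LAL in one eye and Control lens in the other eye" and that "a sample size of 100 bilateral subjects at Postop Month 6 will be sufficient for the study". It sizes the trial on effectiveness endpoints only and refers to the earlier PMA for safety.

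**The concern.** The rule treats a failure to show an excess as evidence that there is none. A low enough count could support a statement that the rate is not higher, but the rule does not ask for one. It asks only that the count stay at or below a ceiling. With about 110 eyes and uncommon events, a count under the ceiling can easily arise when the true rate is well above the benchmark.

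Section 8.6 sets up its other safety comparison the right way round. For endothelial cell loss the null hypothesis is a mean difference of 5% or more, the alternative is less than 5%, power is tabulated, and a one-sided 95% upper limit is compared with the margin. The adverse-event rule reverses that burden of proof without saying so.

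Incidence of ocular serious adverse events, including the ISO events, is the listed safety parameter (section 5.2). Followed as written, the report would make a positive safety statement for each ISO category that the data need not support.

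**Working it through.** **The plan's own figures.** The adverse-event rule has no stated maximum, rate or power to reproduce. Two neighbouring figures were checked.

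- LAL eyes: 100 subjects at Month 6 plus 10% gives 100 × 1.10 = 110, as stated. Dividing by the retained fraction gives 100 / 0.90 = 111.1, so 112. The difference is immaterial here.
- Endothelial cell loss: a one-sample noncentral t calculation with n = 100, SD 4%, margin 5% and one-sided 0.05 gives power 0.981 at a true 3.5% and 0.799 at 4.0%. The plan states 0.98 and 0.80.

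**Inputs for the rule.**

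- n = 110 LAL eyes (section 8.1), repeated at 100 (Month 6) and 120 (the most attempted, section 8.1).
- SPE rates: not in the documents. Assumed range 0.1% to 5%.
- Significance level: inferred. A two-sided 90% interval corresponds to one-sided (1 − 0.90)/2 = 0.05.

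**Two readings of the maximum c.**

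- Test reading: c is the largest count not significantly above the SPE rate, that is, the smallest c with P(X > c | n, SPE) < 0.05.
- Literal reading: c is the largest count whose observed rate does not exceed the SPE rate, c = floor(n × SPE).

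**Formulas.** The exact (Clopper-Pearson) one-sided 95% upper limit at c is U = Beta⁻¹(0.95; c + 1, n − c). The chance of passing at a doubled rate is P(X ≤ c | n, 2 × SPE).

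**Results, n = 110.**

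| Assumed SPE | Test: max (observed rate) | Upper limit | Passes at 2 × SPE | Literal: max | Upper limit | Passes at 2 × SPE |
|---|---|---|---|---|---|---|
| 0.1% | 1 (0.91%) | 4.24% | 0.98 | 0 | 2.69% | 0.80 |
| 0.3% | 1 (0.91%) | 4.24% | 0.86 | 0 | 2.69% | 0.52 |
| 0.5% | 2 (1.82%) | 5.61% | 0.90 | 0 | 2.69% | 0.33 |
| 1% | 3 (2.73%) | 6.90% | 0.82 | 1 | 4.24% | 0.35 |
| 2% | 5 (4.55%) | 9.32% | 0.72 | 2 | 5.61% | 0.18 |
| 3% | 6 (5.45%) | 10.48% | 0.51 | 3 | 6.90% | 0.10 |
| 5% | 9 (8.18%) | 13.84% | 0.33 | 5 | 9.32% | 0.03 |

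In every row, on both readings, the upper limit at the permitted maximum is above the SPE rate.

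**Other sample sizes, SPE 1%, 2%, 3%.**

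- n = 100, test reading: maxima 3, 5, 6; upper limits 7.57%, 10.23%, 11.50%; a doubled rate passes 0.86, 0.79, 0.61.
- n = 120, test reading: maxima 3, 5, 7; upper limits 6.33%, 8.56%, 10.68%; a doubled rate passes 0.78, 0.65, 0.57.
- Literal reading: maxima 1, 2, 3 at both sizes. A doubled rate passes 0.40, 0.23, 0.14 at n = 100 and 0.31, 0.14, 0.07 at n = 120.

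**Zero events.** With 0 of 110 eyes, U = 1 − 0.05^(1/110) = 2.69% (2.95% at 100 eyes, 2.47% at 120).

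**The case against.** **The uncertainty is already reported.** The two-sided 95% interval planned for each reported event has a higher upper end than a one-sided 95% limit. At 3, 5 and 6 of 110 the exact upper ends are 7.8%, 10.3% and 11.5%, against 6.9%, 9.3% and 10.5%. This stands, and it limits the harm. But the interval is tied to reported events, so an ISO category with no cases may get none, and the rule draws its conclusion without using it.

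**The significance-test reading is an inference.** Section 8.6 does not use the word significant for the maximum, and the reference to a one-sided test belongs to BCDVA loss. This stands too. A reader might infer that the permitted maximum necessarily lies above the SPE rate, so that the claim could be made with an observed excess. That is true only on the test reading. On the literal reading the observed rate never exceeds the SPE rate and the pass rates at a doubled rate are much lower. The upper limit still exceeds the SPE rate, so the logical fault remains.

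**The rule comes from ISO and decides nothing.** It is not a study success criterion, and section 8.1 points to the PMA for safety. Both are fair. They justify the count as a screen, but do not turn a count under the ceiling into evidence of no excess.

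**A follow-up mismatch might be inferred.** Section 2.1 mentions "threshold rates calculated from the 1-year historical grid for intraocular lenses", while the events here are counted to Month 6. The documents do not support that criticism: section 2.1 describes the grid used for the earlier 12-month trial, nothing says that the SPE rates in 8.6 are 1-year rates, and 8.6 already states its 6-month basis.

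**Conclusion.** Wrong as written, in the conclusion and not in the counting. A count at or below the maximum permits the statement that no excess over the SPE rate was detected, and no more. This holds on both readings of the maximum, at 100, 110 and 120 eyes, and for every assumed SPE rate from 0.1% to 5%.

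The size is conditional. It depends on SPE rates that the documents do not give and on how the maximum is set. At assumed rates of 1% to 3% and 110 eyes, the chance of declaring a doubled rate not higher runs from 51% to 82% on the test reading and from 10% to 35% on the literal one.

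A reader might go further and say that the trial will pass off a raised rate of sight-threatening events as acceptable, or that the LAL rate is several times the benchmark. The documents support neither. The interval estimates would be visible for reported events, the actual benchmarks are unknown here, and the fault concerns what may be claimed, not what the rate is.

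**What to change.** In section 8.6, keep the ISO maximum as a screen, state how it is calculated (formula and significance level) and list the SPE rates used. Replace the conclusion with: *the LAL rate was not shown to exceed the SPE rate*.

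Show the exact confidence limit beside each ISO count, including events with zero cases. Add a note that even 0 of 110 eyes leaves a one-sided 95% upper limit of about 2.7%.

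It would not help to allow the stronger statement only where the upper limit lies at or below the SPE rate. With 110 eyes that could never be met for an SPE rate below about 2.7%. With zero events it would take 299 eyes at 1% and 149 at 2%.

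The cost is a change of wording and a column in the safety table, with no new data, visits or subjects. The safety statement becomes less favourable.
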